This is a single-center, placebo-controlled, double-blinded, parallel-group, randomized 90 days (+/- 5 days) trial to study the effect of IC-CBAS 500 mg and 1000 mg BID on EEC function, satiety perception, body weight and satiety GI hormones, in patients with APS-OB phenotype. A lifestyle intervention will be provided. These consist of an obesity physician consult, a low-calorie diet instructed by a member of the study team, and physical activity and behavioral suggestions. These interventions should last at least the length of the study. In addition, this study will include 2 colonoscopies at the beginning (i.e., before medication/placebo start) and at the end of the study (i.e., after last dose of medication/placebo) in the first 6 patients in each group willing to consent to the colonoscopies (12 patients; 24 colonoscopies in total). Participants will receive a bowel prep (Movi-prep) and follow standard colonoscopy preparation guides. The next day, after an overnight fasting, a colonoscopy with terminal ileum intubation will be performed. The colonoscopy will be done in the GI clinical or research unit and will be supported by sedation based on patients' characteristics (i.e., conscious sedation vs. anesthesia supported sedation). During the procedure, 8 biopsies will be obtained from the ilium, right and left colon. We will include otherwise healthy patients with a BMI > 30 kg/m², age range 18-65 years, and APS-OB phenotype. Based on the results of our previous trial comparing weight loss in exenatide therapy vs placebo [2], we calculated a sample size of 18 participants per group (total of 36) with 80% power, 0.05 alpha to detect a 1 kg difference between treatment and placebo groups.

Study Intervention:

Ileocolonic-release conjugated bile acid 500mg tablets will be provided by Bilarm Health Inc., San Diego, CA.

Anticipated Results:

In comparison with placebo, IC-CBAS will result in improved EEC function, increased postprandial incretin secretion, and weight loss when compared to placebo.

Significance:

We expect to demonstrate that delayed IC-CBAS increases satiety, restoring satiety in patients with APS-OB phenotype. This study will provide the basis for future pharmacological studies, exploring the effect of luminal enteroendocrine secretagogues in patients with obesity and APS-OB phenotype.

BACKGROUND:

Overview:

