We propose a single center, placebo-controlled, randomized double blinded 90 (+/- 5) day trial, to study the effect of IC-CBAS delivery (500 mg BID for the first week and 1000 mg BID for the rest of the study) on colonic EEC function, postprandial incretins (GLP-1, PYY₃₋₃₆, FGF-19, and OXM), body weight, and satiety (evaluated with gastric emptying and appetite based VAS) in patients with obesity and abnormal satiety. We plan to randomize 18 participants per group. Participants will complete the following visits: 1) Screening and Consent (virtual); 2) Baseline phenotype, lifestyle intervention, 3) Colonoscopy and Randomization visit prior to medication start (in first 6 patients in each arm) who are willing to consent to colonoscopy), 4) Two (in person or virtual) Study Team visits at 30 & 60 days post randomization, 5) Colonoscopy visit and 6) Exit Phenotype visit after taking last medication dose (in first 6 patients in each arm). During the phenotype visits, participants will be phenotyped by measuring energy expenditure, satiety with gastric emptying of solids and VAS scores, satiation with calories consumed to fullness, and emotional eating by questionnaires[8]. Resting energy expenditure will be measured by indirect calorimetry, gastric emptying will be assessed with scintigraphy and calories to fullness will be tested in *ad libitum* meal. In addition, participants will have a body composition with a DEXA scan. Blood will be collected every 30 minutes for 6 hours and selected plasma gastrointestinal hormones will be measured. A sample will be stored for venous blood DNA analysis. Stool samples will be collected for 24 hours for microbiome, bile acids and short chain fatty acids. Participants will keep a food, medication, and activity diary. Participants

will receive a bowel prep (Movi-prep) and follow standard colonoscopy preparation guides. The next day, after an overnight fasting, a colonoscopy with terminal ileum intubation will be performed. The colonoscopy will be done in the GI clinical or research unit and will be supported by sedation based on patients' characteristics (i.e., conscious sedation vs. anesthesia supported sedation). During the procedure, 8 biopsies will be obtained from the ilium, right and left colon. During the Study Team visits, patients will meet with the study team to review medication compliance, assess adverse events, and perform a medication dispensation.

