During the screening and consent visit, informed consent will be requested either in person or virtually through the e-consent process. We will request medical history, or perform a brief chart review if available, acquire most recent anthropometric parameters, (height, weight, and waist circumference) and we will request completion of questionnaires (Appendix A). The questionnaires will be administered via Redcap and will need to be filled after consenting to determine eligibility. Food and activity diaries will be given to the participants for filling during the following 7 days (baseline and treatment phase). An activity tracking device will also be given to be used throughout the complete study. A stool collection kit be provided to complete 48 hours prior to visit 1.

See appendix A: Questionnaires

Screening & phenotyping questionnaires:

1. GI Screening Bowel Disease Questionnaire
2. Hospital Anxiety and Depression Inventory
3. Bristol stool scale
4. Physical Activity Questionnaire
5. Eating Patterns Questionnaire
6. Body Self Relations Questionnaire

7. Audit C Questionnaire
8. Weight Management Questionnaire
9. Obesity Questionnaire
10. Exercise Regulations (BREQ-3) Questionnaire(survey)
11. Barriers to Being Active Questionnaire(survey)
12. Weight Efficacy Questionnaire(survey)
13. Three Factor Eating (TFEQ-R21) Questionnaire(survey)
- 14. Physical Exam and History Documentation**

Baseline phenotype:

Subjects will collect a random stool specimen 48 hours before visit 1. All the participants will be given an activity tracking device. This device needs to be picked up in the CRTU, alongside with the instructions on how to install it with its corresponding tracking app. They will be required to use this device during the time they are participating in the study. Physical activity data, caloric consumption and medication use will be entered by the participants via weekly diaries, as well as extracting physical activity data from each participant's tracking device account. A food diary will also be given to all participants to fill in the week prior during this week. All questionnaires will be sent and filled during this 7-day period in case they didn't complete them during the screening and consent.

- **Visit 1:** Baseline phenotype

Participants will attend Mayo Clinic Clinical Research Trial Unit (CRTU) at [REDACTED] Rochester MN after an 8-hour fasting period.

- They will undergo anthropometric measurements:

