Height, weight, blood pressure, heart and respiratory rates, waist and hip ratio, waist circumference, and temperature.
- Baseline and follow-up characteristics studies:
- Methods of metabolic studies:
 - o Body composition will be measured by DEXA (dual energy x-ray absorptiometry).
 - o Resting energy expenditure was assessed by indirect calorimetry with a ventilated hood (Parvo Medics, Sandy, UT).

- Gastric emptying (GE) of solids by scintigraphy [9] [8, 11] Images will be acquired at 0, 30, 60, 90, 120 and 240 minutes following the normal clinical gastric emptying testing protocol without a push meal.
- Satiation will be measured by *ad-libitum* meal to measure total caloric intake and macronutrient distribution in the chosen food. Satiation will be reported in calories consumed at fullness (satiation) [8] [11].
- Appetite sensations by visual analog score fasting and every 30 minutes after the standard meal for GE and the Satiation test up to 2 hours [8, 11].
- Blood samples: The fasting blood samples will be collected during the gastric emptying meal and stored at -70° C freezer. We will analyze plasma glucose, insulin, C-peptide, GLP-1, PYY₃₋₃₆, OXM, FGF-19, 7- α -C4, Adiponectin, Leptin, CCK, Pancreatic Polypeptide (PP), serum bile acids, short chain fatty acids, amino acids[2, 8]. Samples collection, handling, and storage: Samples will be collected after an overnight fast (of at least 8 hours) in the morning. Plasma will be preserved following standard guidelines and protein degradation inhibitors, kallikrein and DPP-IV inhibitors will be added to preserve the samples. Samples will be stored at -80°C in the PI's laboratory. Plasma hormones and proteomics by radioimmunoassay and/or mass spectrometry measured fasting, postprandial, and every 30 minutes for 6 hours. The primary endpoint being the peak postprandial level (test should be done simultaneously to GE).
- Blood DNA for genome wide association studies (GWAS). These samples will be stored for future research.
- Stool samples: One random stool will be collected at baseline and after treatment for fecal bile acids, short chains fatty acids and microbiome.
- Participants with childbearing potential will undergo a pregnancy test.
- Self-administered questionnaires assessing affect, physical activity levels, attitudes, body image, diet, and eating behavior; details of each questionnaire are provided below.

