- Participants will meet with the study team (either in person at the CRTU or virtually) approximately 30 days after visit 2. The study team will assess adverse events, medication compliance, and perform a new medication dispensation (if visit is virtual the medication will be shipped to the participant's preferred address).

- **Visit 4: Study Team visit**

Participants will meet with the study team (either in person at the CRTU or virtually) approximately 30 days after visit 3. The study team will assess adverse events, medication compliance, and perform a new medication dispensation (if visit is virtual the medication will be shipped to the participant's preferred address).

- **Visit 5: Colonoscopy #2**

- Visit 5 will only be completed in the first 6 patients of each group who are willing to consent to both colonoscopy visits.
 - Participants will receive a bowel prep (Movi-prep) during visit 5 and follow standard colonoscopy preparation guides. The next day, after an overnight fasting, a colonoscopy with terminal ileum intubation will be performed. The colonoscopy will be done in the GI clinical or research unit and will be supported by sedation based on patients' characteristics (i.e., conscious sedation vs. anesthesia supported sedation). During the procedure, 8 biopsies will be obtained from the ilium, right and left colon.

- **Visit 6 – Exit Phenotyping**

- Visit 6 will occur within 7 days of Visit 3. Phenotyping will be performed as at the baseline phenotyping visit including the questionnaires performed in screening visit.

Primary Endpoint:

The primary endpoint is EEC function measured through satiety hormones' (GLP-1 & PYY AUC and absolute plasma value curves) comparison between intervention and placebo groups at day 90 in APS-OB phenotype participants.

Secondary Endpoint:

Evaluation of obesity phenotypes through gastric emptying T_{1/2} for solids, satiety sensation with a visual analogue scale (VAS), fullness (VAS), hunger (VAS), desire to eat (VAS), appetite overall score (VAS), ad-libitum buffet meal food intake (kcal), microbial changes, behavioral questionnaires, energy expenditure, and body weight in APS-OB phenotype participants intervened with IC-CBAS, compared to placebo.

Statistical Analysis:

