The primary analysis will compare AUC values between treatment and placebo groups after 90 days of IC-CBAS. Based on the previous study by Calderon et al.[1], we calculated a sample size of 36 subjects. They reported GLP-1 AUC significant difference between intervention and placebo group of 3223 mg/dl. We aim to detect a mean difference in AUC of 3223mg/dl and utilized their IQR to calculate a standard deviation of 3125mg/dl. To have 80% power to detect a difference of 3223mg/dl with a two-sample t-test would require 12 subjects per group. In order to allow for up to 30% dropout, we will enroll 36 subjects total. The effect on weight loss will be evaluated using analysis of covariance (ANCOVA) models, with relative weight loss as the dependent variable, adjusting for gastric emptying (T_{1/2}, min) and gender. Any power lost on degrees of freedom spent on covariate parameter estimation should be more than reclaimed by reduced error variation. For the rest of the endpoints we will compare the data on gastric emptying, satiation parameters, appetite scores, body composition, energy expenditure, GI hormones, bile acids and microbiota between intervention vs. placebo, using the same ANCOVA model. Transformations will be employed as needed for heavily skewed distributions. All treatment effect estimates will be reported with 95% confidence intervals.

POTENTIAL PITFALLS AND PRECAUTIONS TAKEN:

Potential pitfalls of minor significance in this study are:

- **Selection bias** - Participants willing to participate will likely be more motivated to lose weight than the general population. Randomization, double blind will avoid any selection bias;
- **Potential for type II error** - The sample sizes have been based on appropriate statistical power with allowance for drop out. Estimates of variation have been thoroughly characterized in the prior literature from our lab; and other internal and external studies for weight loss at 12 weeks.
- **Feasibility** - We have identified a cohort of people in our community who have obesity, abnormal satiety phenotype, and are willing to participate. We have the experience to successfully recruit 36 participants for the study.

Human Studies Aspects

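### No weight is taken between baseline and exit and no missing-data rule is given, so anyone who leaves early drops out of the weight analysis

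*Combined protocol and SAP*

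**What the plan says.** The Design section describes the Study Team visits in one sentence: "patients will meet with the study team to review medication compliance, assess adverse events, and perform a medication dispensation". The entries for Visits 3 and 4 repeat those three items, "The study team will assess adverse events, medication compliance, and perform a new medication dispensation", and allow the contact to be held "either in person at the CRTU or virtually". Weight is not among them.

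Weight is measured at Visit 1, in the anthropometric list: "Height, weight, blood pressure, heart and respiratory rates, waist and hip ratio, waist circumference, and temperature". It returns only at Visit 6: "Phenotyping will be performed as at the baseline phenotyping visit including the questionnaires performed in screening visit". Nothing else fills the gap. The screening visit takes the most recent weight, the physical examination form has a weight field, and two questionnaires ask for current weight, but all of these belong to screening, baseline or exit. Between visits the plan relies on diaries: "Physical activity data, caloric consumption and medication use will be entered by the participants via weekly diaries". The diary form in Appendix A has fields for doses, steps, calories and exercise, and none for weight.

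In the Statistical Analysis section, relative weight loss is compared by ANCOVA adjusted for gastric emptying T1/2 and gender. Dropout appears only in the sample size: "In order to allow for up to 30% dropout, we will enroll 36 subjects total". No analysis set, imputation method or early-termination measurement is given. The synopsis separately justifies 18 per group by weight, "to detect a 1 kg difference between treatment and placebo groups", and does not mention dropout.

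**The concern.** A participant who attends day 30 or day 60 and then leaves has been seen by the team on treatment, yet supplies no weight to the analysis. That has two consequences. The comparison rests on fewer people. It is also exposed to selective dropout: the Human Studies section lists nausea, diarrhea and anorexia as possible adverse effects, and the pitfalls section expects volunteers to be motivated to lose weight, so leaving could be related to tolerability or to disappointing weight loss. The pitfalls section relies on randomization and blinding against selection bias, but neither protects against losses after randomization. Weights not recorded at days 30 and 60 cannot be recovered when the data are analysed.

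**Working it through.** **The plan's own figure.** The Statistical Analysis section needs 12 evaluable per group for GLP-1 AUC (taken as stated here). With 30% dropout, 12 / 0.70 = 17.1, rounded up to 18 per group and 36 in total. This matches the plan.

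**Completers at the allowance.** 18 × 0.70 = 12.6 per arm. The standard error of the difference rises by √(18/12.6) = 1.20.

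**Power for 1 kg.** The documents give no SD for weight. The SD implied by 80% power, two-sided alpha 0.05 and 18 per group is 1 / [(1.960 + 0.842) × √(2/18)] = 1.07 kg. At 12.6 per arm, SE = 1.07 × √(2/12.6) = 0.427, and power = Φ(1/0.427 − 1.960) = Φ(0.384) = 65%. Dropout itself causes this fall. Interim weights can recover only part of it.

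**What interim weights would recover.** Let n1, n2 and n3 be the numbers per arm with a day-30, day-60 and day-90 weight. Let r13, r23 and r12 be the correlations between weight changes at those visits. With monotone dropout and a known covariance, in units of the day-90 variance,

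Var = (1 − R²)/n3 + (R² − r13²)/n2 + r13²/n1, where R² = (r13² + r23² − 2·r13·r23·r12)/(1 − r12²).

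Effective n is 1/Var. The correlations and dropout timing are assumptions, because the documents give neither.

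| Case | r13, r23, r12 | Dropouts before day 30 / days 30–60 / after day 60 | Effective n | SE against completers | Power, 1 kg |
|---|---|---|---|---|---|
| Low | 0.50, 0.70, 0.70 | 60 / 20 / 20% | 13.3 | 3% lower | 67% |
| Central | 0.65, 0.85, 0.85 | one third each | 14.6 | 7% lower | 71% |
| High | 0.80, 0.95, 0.90 | 20 / 30 / 50% | 16.0 | 11% lower | 75% |
| All leave before day 30 | any of these | 100 / 0 / 0% | 12.6 | no change | 65% |

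Central case in full: n1 = 16.2, n2 = 14.4, n3 = 12.6 and R² = 0.741. Var = 0.259/12.6 + 0.319/14.4 + 0.4225/16.2 = 0.0687, so effective n = 14.6 and the SE ratio is √(12.6 × 0.0687) = 0.93.

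**Selective dropout.** Simulation with an assumed day-90 SD of 4 percentage points, about one third dropping out, adjacent-visit correlations of 0.70–0.92, and one logistic rule for both arms in which a smaller recorded loss raises the chance of leaving:

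- Mild to moderate dependence: the completers' difference is too small by about 3–11% of the effect. At a true 1-point difference (1 kg at an assumed 100 kg) that is about 0.02–0.12 points.
- Stronger dependence: about 0.15–0.22 points at the same effect.
- The likelihood estimate using interim weights is close to unbiased in these settings.
- If the dropout rate and the selection relative to the arm's own mean are the same in both arms, the completers' bias cancels.
- If poor early losers leave in one arm only, a true 1.00 kg appears as about 0.82 to 1.25 kg.

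For scale, the completers' SE is 4 × √(2/12.6) = 1.59 points, so a bias of 0.12 points is 0.12/1.59 = 0.08 SE.

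**The case against.** The primary endpoint is GLP-1 and PYY at day 90. Weight closes a long list of secondary endpoints in a trial that presents itself as proof of concept. The dropout allowance is an upper limit and was set for GLP-1 AUC. A single-time-point ANCOVA is a common choice for a secondary endpoint in 36 people. The precision gain is small and vanishes if people leave before day 30, which is plausible for tolerability dropout. Both visits may be virtual, so many interim weights could be home readings, and a repeated-measures model with about 12–13 completers per arm needs care over interval coverage. An exit weight for everyone who withdraws would meet part of the concern by itself.

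All of this stands, and it limits the size of the point. It does not supply the missing weights: no section provides one between baseline and exit, or says what happens to a participant without a day-90 value.

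A reader might infer that the plan prescribes a completers analysis. It does not say so; this follows from the visit schedule, the model and the absence of a missing-data rule. A reader might also infer that the weight result will be biased. The documents give no dropout pattern, and the bias ranges from nil to material depending on that pattern.

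**Conclusion.** The concern holds as a modest, inexpensive improvement to a secondary analysis. As written, an early leaver has no post-baseline weight, and the weight comparison is in effect restricted to completers. At the full 30% allowance, interim weights would lower the SE by about 3–11% and raise power for 1 kg from about 65% to 67–75%. They would also remove a completers' bias of about 3–11% of the effect when dropout depends mildly to moderately on recorded weight, and more when the dependence is stronger. These figures rest on assumed correlations, dropout timing and SDs: 1.07 kg back-calculated for power and 4 points for bias.

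Two stronger conclusions are not supported. Interim weights would not restore the nominal 80% power. They also leave the primary hormone endpoint untouched, since it too is lost for anyone missing at day 90. There is no gain for dropouts before day 30, and no protection when leaving depends on factors that are not recorded.

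**What to change.** - Add body weight to the Visit 3 and Visit 4 entries: clinic scale if in person, dated home-scale weight under a written standard procedure if virtual. Record a weight at early withdrawal too.
- Ask participants who stop study medication to attend the day-90 exit visit anyway. This step would also help the primary endpoint.
- Estimate the day-90 difference in relative weight change with a repeated-measures likelihood model (treatment by visit, baseline weight, baseline T1/2, sex) and a small-sample correction such as Kenward-Roger. Baseline weight is an addition to the planned covariates.
- Keep the planned ANCOVA as a sensitivity analysis, and state the analysis set and how missing weights are handled.
- While editing the visit entries, reconcile the timing of Visit 6: its entry ties it to within 7 days of Visit 3, whereas the Methods section places the exit visit at day 90.

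The cost is about one line per visit entry, a short home-weighing instruction and a standard model. The contacts already exist. The downside is that home weights are noisier than clinic weights and the model is slightly more complex. A check that excludes home weights would show how far they matter, but it moves back toward the completers analysis.

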- VI. Any acute or chronic condition or other disease that, in the opinion of the Investigator, would limit the subject's ability to complete and/or participate in this clinical study.
- VII. Significant untreated psychiatric dysfunction based upon screening. Hospital Anxiety and Depression Inventory (HAD) score >11 on depression scale, a self-administered alcoholism screening test (AUDIT-C) score >4 in men or >3 in women, and difficulties with substance or eating disorders determined by the Questionnaire on Eating and Weight Patterns (binge eating disorders and bulimia); will mean the participant will be excluded and given a referral letter to his/her primary care doctor for further appraisal and follow-up. The provider will review the patient's alcohol intake over the past few months to confirm accuracy and determine study eligibility.

VII. Principal Investigator discretion.

[figure not shown]
Intervention:

CBAS 500 mg tablets will be supplied by Bilarm Health Inc.. Subjects will take medication or placebo orally twice daily on an empty stomach, 30 minutes prior to breakfast and evening dinner for 90 +/- 5 days. Patients on the medication will receive 500 mg twice daily during their first week and 1000 mg twice daily for the rest of the study.

Methods:

Participants will keep food, appetite, and activity diaries for one week prior to baseline test day[11]. On randomization day they will also receive the randomized medication (delayed release IC-CBAS or placebo). A full medical history and physical exam will be performed and recorded, and a low-calorie diet will be suggested during this visit.

On Day 90 (+/- 5 days), subjects will repeat obesity phenotyping protocol at the exit visit [11] as described previously but will receive the study medication/placebo 30 minutes prior to the test meal.

*Visit 1, 3, 4 and 6 can be conducted at the Clinical Research and Trials Unit (CRTU)in the [REDACTED] at Mayo Clinic in Rochester, MN.

Visit 2 and 5 can be conducted at the CRTU or on [REDACTED]

Screening and Consent (virtual):

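### The Visit 6 timing rule puts exit phenotyping at about day 23 to 37, which cannot be squared with the day 85 to 95 window and the day-90 primary endpoint set elsewhere in the plan

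*Combined protocol and SAP*

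**What the plan says.** All references are to the combined protocol and SAP.

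- **Visit 6 – Exit Phenotyping:** "Visit 6 will occur within 7 days of Visit 3", and "Phenotyping will be performed as at the baseline phenotyping visit".
- **Visit 1, blood samples:** the phenotyping visit includes hormones "measured fasting, postprandial, and every 30 minutes for 6 hours". Visits 3 and 4 list no blood sampling and Visit 5 is a colonoscopy, so Visit 6 supplies the post-baseline AUC.
- **Visit 3 and Visit 4:** "approximately 30 days after visit 2" and "approximately 30 days after visit 3" respectively. The Design section gives the same spacing, days 30 and 60, counted from randomization.
- **Methods:** "On Day 90 (+/- 5 days), subjects will repeat obesity phenotyping protocol at the exit visit".
- **Primary Endpoint:** "comparison between intervention and placebo groups at day 90 in APS-OB phenotype participants".
- **Statistical Analysis:** "The primary analysis will compare AUC values between treatment and placebo groups after 90 days of IC-CBAS".

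On who attends, the Visit 2 section contains randomization and medication hand-out but restricts the visit to the colonoscopy subset, six per arm. Item 3 of the visit list in Design carries the same restriction. Design also randomizes 18 per group, 36 in all.

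**The concern.** The plan gives two timings for the visit that produces its primary endpoint, and they are about two months apart. Staff working from the visit descriptions find a Visit 6 rule that contradicts Methods. Whatever day is chosen, the visit departs from one of the two written windows. Until one rule is fixed, nobody can say which exit visits are protocol deviations for the primary endpoint.

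A second, smaller matter is the starting point of the count. The visit descriptions count Visit 3 from Visit 2 and start medication after it, yet Visit 2 as written belongs to only 12 of the 36 participants. Methods does not say what its day 90 is counted from.

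**Working it through.** No sample-size or power formula bears on this point; the check is calendar arithmetic. Take day 0 as Visit 2, where randomization sits and after which medication starts.

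**The plan's own schedule, reproduced**

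- Visit 3: about 0 + 30 = day 30.
- Visit 4: about 30 + 30 = day 60. Both agree with the Design section.
- Exit visit under Methods: 90 − 5 = 85 and 90 + 5 = 95, so day 85 to 95.

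**The Visit 6 rule**

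- Seven days either side of Visit 3: 30 − 7 = 23 and 30 + 7 = 37, so about day 23 to 37.
- Read as after Visit 3 only: day 30 to 37.
- The latest day allowed falls before Visit 4 by 60 − 37 = 23 days.

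**Comparison**

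- Gap at the nearest edges: 85 − 37 = 48 days.
- Nominal gap: 90 − 30 = 60 days.
- Visit 3 is only approximately at day 30. If it varies by 5 days (an assumption), the latest Visit 6 falls at day 32 to 42, and the gap is 85 − 42 = 43 to 85 − 32 = 53 days.
- For a rule of seven days either side to touch day 85 to 95, its anchor visit must fall between 85 − 7 = 78 and 95 + 7 = 102. Visit 3 does not come near that.

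**Would changing only the visit number be enough?** This bears on the fix, not on the size of the problem. Visit 4 as anchor gives 60 − 7 = 53 to 60 + 7 = 67, still short of day 85. Visit 5 has no numbered day, and it does not exist for 36 − 12 = 24 participants.

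**The colonoscopy subset (6 × 2 = 12 participants)**

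- Treatment may run to 90 + 5 = day 95 (Visit 2 section).
- Study design places colonoscopy #2 after the last dose.
- Design and the visit descriptions list exit phenotyping after that colonoscopy, while Methods has study medication given before the exit test meal.
- Taken in the listed order, a participant treated to day 95 would have exit phenotyping after day 95, outside the Methods window. One whose treatment ended at day 85 would have 95 − 85 = 10 days left. Whether the window can be met therefore depends on passages that do not agree on the order.

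**The case against.** The strongest reply is that this is an obvious wrong visit number. Study design, Design, Methods, the treatment duration under Visit 2, the primary endpoint and the primary analysis all give 90 days. Visit 6 is listed after Visits 4 and 5, Visit 4 still dispenses medication, and the day-90 endpoint follows directly below the Visit 6 text. That stands as evidence of intent, and it limits the severity. It does not make the sentence harmless, because it is current, operative text and the only Visit 6 timing in the visit-by-visit section.

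Some stronger readings are tempting but not supported:

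- A reader might infer that the primary AUC will be measured at about one third of the planned exposure (30/90), or that the comparison is biased. The documents point to day 90 as the intent, nothing in them shows a mistimed visit, and no effect on the estimate can be derived.
- A reader might infer that the 24 participants outside the colonoscopy subset have no schedule. They do: Design counts the study team visits from randomization, and Methods gives the exit window.
- A reader might conclude that the plan requires counting from randomization. Design does so for Visits 3 and 4, but the primary analysis refers to days of treatment, which fits first dose equally well. The documents show no difference in days between the two for any participant.

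**Conclusion.** The contradiction holds. The Visit 6 rule gives about day 23 to 37 and Methods gives day 85 to 95; they are 48 days apart at the nearest edges and cannot both be met. The result assumes that Visit 2 is day 0 and that Visit 3 falls close to day 30. It does not depend on whether the seven days run both ways or only forward.

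This is an internal inconsistency that should be fixed, not a design choice. That it is a stale reference is an inference, though a well-supported one. The day-0 wording and the order of procedures in the colonoscopy subset are secondary: the first is a drafting fault with no shown difference in days, and the second concerns up to 12 of 36 participants (33%), with no effect that can be quantified from the documents.

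**What to change.** 1. Replace the Visit 6 sentence with the day 90 (± 5) window already in Methods.
2. State one day 0 for that window that exists for all 36 participants. Randomization or first dose would serve; the choice is the sponsor's.
3. Correct both the Visit 2 section and item 3 of the visit list in Design, so that randomization, medication hand-out and the count to Visit 3 apply to everyone and only the colonoscopy is limited to the subset. Design carries the same restriction, so it cannot serve as the reference text here.
4. Reconcile Study design, Design, Methods and the Visit 2, Visit 5 and Visit 6 sections on the order of last dose, colonoscopy #2 and exit phenotyping in the colonoscopy subset, so that the day 85 to 95 window can be met. No order or dosing is proposed here.

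Items 1 to 3 cost one replaced sentence, one added sentence and a relabelled visit in two places, with no added visits or procedures. Item 4 needs a decision by the study team, and its cost cannot be estimated from the documents.
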